## 10.10 Safety Analyses

Assessment of safety will primarily be based on the incidence and severity of complications and adverse reactions associated with the treatment. Adverse event rates will be summarized by type of AE and for specific AEs in two ways: 1) per patient using counts and percentages and 2) by event, summarizing event counts by visit interval over time. Device and procedure related events will be summarized by severity. Events listings will be provided that include details such as relatedness, severity, onset and resolution status will be provide for all events and for relevant subsets of events such as serious events and related events.

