## **5 Study Overview**

### **5.1 Purpose**

The purpose of this study is to demonstrate that the success rate of the Study group receiving the Superior® Interspinous Spacer is not inferior to the success rate observed in the X-STOP® IPD® control group at 60 months follow-up, and that the Superior® Interspinous Spacer is safe when used in the treatment of moderately impaired LSS patients. This safety and effectiveness data will be used to satisfy the Agency-imposed Conditions of Approval of the Superior® Premarket Approval (PMA).

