### 5.2.3 Safety Endpoints and Role of CEC

Data will be evaluated for safety endpoints by an independent Clinical Events Committee (CEC). Safety outcomes will be determined by evaluating the type, frequency, severity, and relationship to device of adverse events through the 60-month time point for all subjects. Adverse events will be categorized as implant-related or procedure-related. All device-related events and major procedure-related failures reported by the site PIs will be adjudicated by the independent CEC. In addition, events reported as having unknown or undetermined relationship to the device by the site PI will be adjudicated by the CEC.

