### 10 Statistical Considerations and Methodology

#### 10.1 Clinical Trial Objective

The objective of this trial is to show that the Superior® Interspinous Spacer is safe and non-inferior in efficacy compared to the X-STOP® IPD® device in patients with moderate lumbar spinal stenosis at 60 months post-treatment.

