## 10.9 Secondary Endpoints

Secondary continuous effectiveness endpoints will be summarized by treatment group over time and as changes over time with descriptive statistics including means, standard deviations, median, minimum and maximum values. Secondary categorical effectiveness endpoints will be summarized by treatment group over time using counts and percentages. Descriptive effect size measures such as standardized mean differences will be presented as an aid in comparing magnitudes of groups differences across endpoints measured on different scales. Secondary endpoints analyses may also include other traditional frequentist confidence intervals and p-values for superiority.

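### The protocol sets out to show that Superion is safe at 60 months, but section 10.10 pre-specifies only descriptive tables: no principal safety outcome, between-arm estimate, interval or criterion

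*Combined protocol and SAP*

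**What the plan says.** **The aim.** Section 5.1 gives two things to be demonstrated: non-inferior success, and that the "Interspinous Spacer is safe when used in the treatment of moderately impaired LSS patients". The synopsis says the same for 5 years post-surgery. Section 10.1 restates the aim as showing that the "Interspinous Spacer is safe and non-inferior in efficacy compared to the X-STOP" device at 60 months.

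**The safety endpoints.** The synopsis and section 5.2.3 define them: "Safety outcomes will be determined by evaluating the type, frequency, severity, and relationship to device of adverse events through the 60-month time point". Device-related events and major procedure-related failures reported by sites "will be adjudicated by the independent CEC", as do events whose relationship to the device is unknown. Section 10.4 makes the mITT population the basis for all safety data.

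**The safety analysis.** Section 10.10 opens: "Assessment of safety will primarily be based on the incidence and severity of complications and adverse reactions associated with the treatment". Adverse event rates are to be summarized "per patient using counts and percentages and 2) by event, summarizing event counts by visit interval over time", with related events tabulated by severity and with event listings. Unlike section 10.9, it does not say that summaries are by treatment group. Intervals are mentioned only in section 10.9, as an option: "Secondary endpoints analyses may also include other traditional frequentist confidence intervals and p-values for superiority".

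**The effectiveness analysis, for contrast.** Sections 10.2 and 10.5 give a defined responder, a margin of -0.10, Beta(1,1) priors and a posterior threshold of 0.95.

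**The concern.** The verb in the objective and the content of the analysis do not match. To demonstrate safety against a randomized control needs at least an outcome to judge it on and an estimate of the difference with its uncertainty. Section 10.10 supplies neither, so the standalone safety statement would rest on reading columns of percentages.

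Two things are at stake. Similar-looking percentages could be taken as similar safety, with nothing in the report to show how large an excess the data leave open. And because no principal outcome is designated beforehand, the events to be emphasized would be chosen after the tables are seen.

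**Working it through.** **1. The plan's own figure.** There is no power or precision figure for safety to reproduce. The only one given is for the composite: 73% power with 155 and 161 patients, success rates of 40% and 37.8%, margin 0.10 and posterior threshold 0.95 (section 10.5).

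- SE = sqrt(0.40×0.60/155 + 0.378×0.622/161) = 0.0549
- z = (0.022 + 0.10)/0.0549 − 1.645 = 0.58, giving power of 71.9%
- Exact enumeration of the Beta(1,1) posterior rule gives 74.3%

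The stated 73% lies between the two. The effectiveness claim therefore has a rule with known properties.

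**2. Can the composite stand in for a safety comparison?** Section 10.2 counts as failures index-level re-operation, revision, removal or supplemental fixation; dislodgement, migration or deformation; neurological deficit; spinous process fracture; deep infection; death; and device-attributed disability. A large excess of these would lower Superion's success rate. There are two limits.

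- Offsetting. Suppose, hypothetically, that such failures cost Superion 5 points of success while ZCQ gains add 5 points. Success is then equal, say 40% in each arm, and the non-inferiority rule is met with probability 59.5% (exact enumeration, 155 and 161). The safety excess does not show in the result.
- Coverage. Adverse events outside the listed components, including serious ones, do not enter the composite.

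**3. What a between-arm interval would show.** Inputs: 182 and 189 patients (section 10.4, after removing the two non-participating sites), or 155 and 161 at the plan's assumed 85% follow-up. Per-patient event rates are **assumed**, because the documents give none.

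95% half-width = 1.96 × sqrt(p(1−p)(1/n1 + 1/n2)), where sqrt(1/182 + 1/189) = 0.1039 and sqrt(1/155 + 1/161) = 0.1125.

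| Assumed rate | 182 vs 189 | 155 vs 161 |
|---|---|---|
| 2% | ±2.8 points | ±3.1 points |
| 5% | ±4.4 | ±4.8 |
| 10% | ±6.1 | ±6.6 |
| 20% | ±8.1 | ±8.8 |

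The 2% row is rough, since it corresponds to about 4 events per arm (0.02 × 182 = 3.6). With 182 and 189 patients, power to detect a 5-point excess (two-sided 0.05) is about 45% at a 5% control rate, 31% at 10% and 21% at 20%.

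For zero events in 182 patients, the one-sided 95% upper bound is 1 − 0.05^(1/182) = 1.6%. The upper limit of a two-sided 95% interval is 1 − 0.025^(1/182) = 2.0%.

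**4. Two details that affect any safety percentage.** Section 9.3 has patients exit the study after index-level surgery, with at most 30 days of further follow-up. Crude percentages would therefore mix patients observed for very different times, and section 10.10 does not address this. Section 10.4 gives both 190/201 and 182/189 without saying which is the safety denominator.

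**The case against.** The strongest reply is that safety is not left unplanned. Endpoints are listed, an independent committee adjudicates the important events, the population is fixed, and the gravest device and procedure failures sit inside a composite that is formally compared between randomized arms. Descriptive adverse event tables are also common practice. All of this stands, and it limits the point.

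A reader might infer three stronger things that the documents do not support.

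- *That no safety outcome is named.* The synopsis and section 5.2.3 name several attributes of adverse events. What is missing is one designated as principal, with an estimate or criterion.
- *That the trial cannot support any safety conclusion.* The randomized data the protocol plans to collect allow the comparison, and the composite gives indirect evidence. The plan omits the direct estimate; the design does not prevent it.
- *That the study would fail its conditions of approval.* Section 5.1 says the data will be used to satisfy them. What the approval order requires is not in the documents, so they cannot show that descriptive reporting falls short.

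The reply does not remove the mismatch. Descriptive tables suit an aim to describe, and this protocol's aim is to demonstrate.

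**Conclusion.** The point holds as a gap between objective and analysis. For the standalone safety claim the plan pre-specifies no principal outcome, between-arm estimate, interval or criterion, and the composite only partly fills the gap.

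The size depends on event rates, which are assumed. With 182 and 189 patients and rates from 2% to 20%, equal observed percentages would leave an excess of about 3 to 8 points open. With 155 and 161 it would be about 3 to 9 points. These figures illustrate precision under simple binomial sampling; they do not show an error in any number in the plan. The primary non-inferiority and superiority analyses are not affected.

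**What to change.** In section 10.10:

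- Name a small set of protocol-defined events as the principal safety outcomes. Candidates are CEC-adjudicated device-related serious adverse events; spinous process fracture; and index-level re-operation, revision, removal or supplemental fixation. The exact choice is the sponsor's, provided it is fixed before the Month 60 data are examined.
- For each, report by randomized arm the cumulative incidence through Month 60 and the Superion minus X-STOP difference with a 95% interval.
- Use a time-to-event cumulative incidence estimate, not a crude binomial proportion, so that loss to follow-up and the exit in section 9.3 are allowed for. Exit after index-level surgery is unlikely to be unrelated to later risk, so for the other outcomes it should be handled explicitly, for example as a competing event.
- State whether the safety denominator is 190/201 or 182/189.

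In the synopsis and sections 5.1 and 10.1, reword the safety aim as estimating and comparing safety through 60 months. If the word demonstrate is kept, a criterion has to be stated with it.

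The cost is a few extra estimates from data the protocol already plans to collect and a more modestly stated objective. No further patients or visits are needed.

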
Number of Sites:
	
Only sites participating in the original IDE study will participate in this continued follow-up protocol. 25 IDE sites remain eligible for participation.

Study Enrollment:
	
Enrollment was completed in December 2011, with 391 randomized and treated patients and 28 non-randomized Superior® training patients.

Study Duration:
	
Subjects included in the original clinical investigation (G070118) returned for follow-up visits at 6 weeks, and 3, 6, 12, 18 and 24 months post-treatment to collect data for the primary evaluation of safety and effectiveness. Patients will be followed annually until each patient has reached the 60 month time point. Study duration is approximately 36 months as all patients have reached 24 months prior to the start of this continued follow-up protocol. Patients may potentially be followed annually for up to 10 years as part of a possible post-approval study.

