#### **5.4 Duration and Extent of Investigation**

Subjects included in the clinical investigation have returned for follow-up visits at 6 weeks ( $\pm 2$  weeks), 3 months ( $\pm 2$  weeks), 6 months ( $\pm 1$  month), 12 months ( $\pm 2$  months), 18 months ( $\pm 2$  months) and 24 months ( $\pm 2$  months) post-treatment to collect data for the primary evaluation of safety and effectiveness. Patients will continue to be followed annually ( $\pm 3$  months) until each patient has reached the 60 month time point. Study duration is anticipated to be extended by approximately 36 months to accommodate this additional follow-up.

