After implantation of the Superior® ISS or the X-STOP® IPD® device, each Investigator provided a postoperative care regimen based on the subject’s specific need. The regimen may have included, but was not limited to: medications, a corset or brace, acupuncture, traction, physical therapy, chiropractic treatment, use of a TENS unit and massage therapy. The type and amount of the postoperative care were collected.

At each follow-up visit through 60 months, subjects will be interviewed to determine if they have experienced adverse events (AEs) since the previous follow-up visit. A neurological assessment will be performed for all patients at baseline and all follow-up visits. All subjects will be required to complete ZCQ, ODI, VAS, SF-12, and the VertiFlex® Patient Satisfaction questionnaires to evaluate disability, function, pain, quality of life and satisfaction at each follow-up visit. Subjects were also required to complete a VAS questionnaire to evaluate pain status at discharge.

The potential impact of spinal injections/nerve blocks use on the ZCQ was evaluated based on review of the medical literature. As these are potentially confounding of the ZCQ outcomes, epidural steroid injections or nerve block procedures at the treated level(s) will be deemed failures. Further, rhizotomy procedures at the treated level(s) will be deemed failures.

---

 Campbell's Operative Orthopedics (11th ed.) at 2281: "Although epidural steroid injections have been used in the treatment of spinal stenosis for many years, no scientifically validated long-term outcomes have been reported to substantiate their use, and most prospective reports show no statistically significant benefit. A meta-analysis showed that epidural steroids have little short-term advantage over placebo for treatment of leg pain." See also Carette S, Marcoux S, Truchon R, Grondin C, Gagnon J, Allard Y, Latulippe M. (1991) A controlled trial of corticosteroid injections into facet joints for chronic low back pain. *NEJM* 325(14):1002-1007. Jackson RP, Jacobs RR, Montesano PX (1988). Facet joint injection in low-back pain: A prospective statistical study. *Spine* 13(9):966-71.

With respect to spinal cord stimulators, because the use of a permanent implant would require a surgical procedure, this will be deemed a study failure.

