### 10.4 Analysis Populations

The study contains two treatment arms with patients receiving either the Superior® ISS or the X-STOP® IPD® device. The following subject groups or analysis populations will be used to complete the analysis of data:

*Modified Intent-to-treat* patient population (mITT): The mITT patient population will include all patients randomized, and with an anesthesia start time recorded, where patients will be classified by the group in which they are randomized, regardless of the treatment received.

*Per protocol* patient population (PP): The PP patient population will include all subjects with 60-month follow-up data and no major protocol deviations and subjects that failed before 60 months and subsequently did not complete 60 months.

The primary efficacy analysis will be conducted on the mITT patient population. Secondary efficacy analyses will be done on the PP population. All safety data will be analyzed based on the mITT patient population.

The numbers of patients in the mITT analysis set included 190 patients randomized to Superior® and 201 patients randomized to the X-STOP® IPD® Control group. Eight (8) Superior® patients and 12 X-STOP® IPD patients are from 2 sites that are not participating in the PAS. This reduces the analysis set to 182 Superior® and 189 X-STOP® IPD®, respectively. Assuming 85% follow-up for the primary effectiveness endpoint at Month 60, there will be 155 Superior® patients and 161 X-STOP® IPD patients included in the primary non-inferiority evaluation.

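### The only by-time adverse event summary in Section 10.10 is raw counts over visit intervals of unequal length, so at a constant event rate the count roughly doubles when the interval goes from 6 to 12 months after Month 24

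*Combined protocol and SAP*

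**What the plan says.** Section 10.10 (Safety Analyses) sets out two tabulations of adverse event rates. The first is "per patient using counts and percentages". The second is "by event, summarizing event counts by visit interval over time". It also plans event listings that show relatedness, severity, onset and resolution. It names no denominator for the second tabulation and does not define a visit interval.

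Section 6 (Study Design) says how events are elicited: at each visit "subjects will be interviewed to determine if they have experienced adverse events (AEs) since the previous follow-up visit". A count attached to a visit therefore accumulates over the whole time since the visit before.

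The Protocol Summary Page gives the schedule. Subjects "returned for follow-up visits at 6 weeks, and 3, 6, 12, 18 and 24 months post-treatment", and after that "Patients will be followed annually until each patient has reached the 60 month time point"; Section 5.4 agrees ("Patients will continue to be followed annually"). The same page states that "all patients have reached 24 months prior to the start of this continued follow-up protocol", so the extension opens at the point where visits become yearly.

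Section 10.4 fixes the safety population: "All safety data will be analyzed based on the mITT patient population".

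**The concern.** A count of events between two visits depends on the event rate, the number of patients under observation and the length of the interval. Section 10.10 reports the count and leaves out the other two. Length is not constant here. It goes from 3 to 6 months at Month 6 and from 6 to 12 months at Month 24, and the second change coincides with the start of the study this protocol governs.

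The study is meant to show that the device is safe through 60 months, under the conditions of approval (Section 5.1). Someone reading the table from left to right will want to know whether events become more or less frequent with time since implantation. As specified, the counts move with visit spacing even if nothing changes clinically and nobody leaves follow-up. Spacing inflates later intervals relative to earlier ones. That can suggest a late increase that is not there, or hide a real late improvement.

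**Working it through.** The documents give no adverse event rate or expected count, so there is no safety figure to reproduce. The patient numbers were checked first: 190 − 8 = 182 and 201 − 12 = 189 patients at participating sites, 371 in total; 0.85 × 182 = 154.7 (stated as 155) and 0.85 × 189 = 160.65 (stated as 161). These agree.

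**Inputs.** Visits at 6 weeks and 3, 6, 12, 18, 24, 36, 48 and 60 months (Protocol Summary Page; Section 5.4). Follow-up of 97% and 95% at 2 years (Section 10.5), and 85% assumed at Month 60 (Section 10.4). Assumption: a constant 20 events per 100 patient-years, which is illustrative and cancels from every ratio.

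**Formula.** Expected count = rate × patients × mean retention over the interval × interval length in years. Mean retention is the average of the values at the two ends.

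**Full retention, 371 patients.** For Month 18-24: 0.2 × 371 × 0.5 = 37.1. For Month 24-36: 0.2 × 371 × 1 = 74.2.

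| Interval (months) | Length (months) | Expected count | Ratio to Month 18-24 |
|---|---|---|---|
| 0 to 1.38 (6 weeks) | 1.38 | 8.6 | 0.23 |
| 1.38 to 3 | 1.62 | 10.0 | 0.27 |
| 3 to 6 | 3 | 18.6 | 0.50 |
| 6 to 12 | 6 | 37.1 | 1.00 |
| 12 to 18 | 6 | 37.1 | 1.00 |
| 18 to 24 | 6 | 37.1 | 1.00 |
| 24 to 36 | 12 | 74.2 | 2.00 |
| 36 to 48 | 12 | 74.2 | 2.00 |
| 48 to 60 | 12 | 74.2 | 2.00 |

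**With the stated follow-up figures.** Pooled retention at Month 24 is (182 × 0.97 + 189 × 0.95) / 371 = 0.960. Taking it as linear from 100% at surgery, and then linear to 85% at Month 60:

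| Interval (months) | Patient-years | Expected count | Ratio to Month 18-24 | Per 100 patient-years |
|---|---|---|---|---|
| 18 to 24 | 179.0 | 35.8 | 1.00 | 20.0 |
| 24 to 36 | 349.3 | 69.9 | 1.95 | 20.0 |
| 36 to 48 | 335.7 | 67.1 | 1.88 | 20.0 |
| 48 to 60 | 322.1 | 64.4 | 1.80 | 20.0 |

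**Variations.**
- If all 391 mITT patients contribute before Month 24 and 371 after, the Month 24-36 ratio is 1.85.
- If Month 60 retention were only 50%, the Month 24-36 ratio would be 1.83, falling to 1.20 by Month 48-60.
- If the true rate halved at Month 24, the Month 24-36 ratio would be 0.5 × 2.00 = 1.00 with full retention and 0.5 × 1.85 = 0.93 with the mixed patient numbers: roughly flat.

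The last column of the second table shows that dividing by patient-years removes the step: the constant rate appears as constant.

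**Interval definition.** With ±2 months at Month 24 and ±3 months at Month 36 (Sections 5.4 and 6.5.4), one patient's Month 24-36 interval can last from 33 − 26 = 7 to 39 − 22 = 17 months. Appendix A instead gives ±2 months for the annual visits, which implies 34 − 26 = 8 to 38 − 22 = 16 months, and it prints a window of 22-26 months under Months 36, 48 and 60.

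**The case against.** The best defence is that the table is accurate as labelled. It is descriptive, with no trend test or decision rule, and the plan does not commit to comparing Months 24-60 with the first two years. The trial's question is Superion against X-STOP, and both arms follow the same schedule. Section 10.10 rests safety mainly on incidence and severity, reports per-patient percentages first, and lists events with their onset. A constant rate is also an idealisation, since procedure-related events would be expected early.

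Much of this stands, and it rules out several stronger readings that a reader might infer:
- **A steadily rising safety signal.** The artefact at Month 24 is one step, followed by a flat or falling count as patients leave.
- **A biased comparison of the devices.** Interval length is common to both arms. Unequal arm sizes (182 and 189) and any differential dropout are separate reasons for a denominator.
- **No other information on timing.** The listings give onset for each event.
- **A concealed late increase.** Longer late intervals inflate late counts; on their own they do not hide a rise.
- **A precise ratio between the yearly and the earliest intervals.** Section 10.10 does not say whether the discharge assessment (0-7 days) opens its own interval, so the length of the first one is not fixed.

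The defence does not remove the gap. The per-patient percentages are not stated by interval or per unit time, and a listing gives dates without a rate. A table laid out over time invites reading over time, and the section itself promises rates.

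**Conclusion.** The concern holds as a limited reporting defect. At a constant event rate, the planned table would show the Month 24-36 count at about 1.85 to 2.0 times the Month 18-24 count for reasons of visit spacing alone, and a true halving of the rate would look roughly unchanged. This rests on scheduled visit times, a constant rate used for illustration, and retention near the stated 97%/95% at Month 24 and 85% at Month 60. The Month 24-36 ratio depends little on retention (1.83 even at 50% by Month 60); the later ratios depend on it more.

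The consequence is confined to describing how event frequency changes with time since implantation. The primary non-inferiority analysis and the superiority test are untouched. The documents do not support a claim that the safety conclusion as a whole is unsound. The change is worth making because it is cheap and gives the section the rates it announces.

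**What to change.** In Section 10.10, keep the event counts and add, for each visit interval and arm, the number of patients at risk, the observed patient-years, and events per 100 patient-years. Assign each event to an interval by its onset date. State that any description of change over time will rest on these rates. A further table in equal 12-month periods is an optional extra.

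Before the intervals are defined, say whether discharge opens its own interval, and reconcile the annual visit windows: ±3 months in Sections 5.4 and 6.5.4, against ±2 months and 22-26 months in Appendix A.

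The cost is a sentence or two in the plan and wider tables. Onset is already among the listed items. Patient-years also need visit and exit dates. The case report forms probably hold these, but the documents do not say so explicitly (Sections 7 and 9.3 mention recording the reason for exit), so this should be confirmed.
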